12.7.2. Vital Signs

Vital Sign Parameter	Units	Clinical Concern Range	
		Lower	Upper
Absolute			
Systolic Blood Pressure	mmHg	< 85	> 160
Diastolic Blood Pressure	mmHg	< 45	> 100
Heart Rate	bpm	< 40	> 110

12.8. Appendix 8: Abbreviations & Trade Marks

12.8.1. Abbreviations

Abbreviation	Description
ADaM	Analysis Data Model
AE	Adverse Event
AESI	Adverse Events of Special Interest
AIC	Akaike's Information Criteria
CDISC	Clinical Data Interchange Standards Consortium
CI	Confidence Interval
CPMS	Clinical Pharmacology Modelling & Simulation
DBF	Database Freeze
DBR	Database Release
DOB	Date of Birth
DP	Decimal Places
EASI	Eczema Area and Severity Index
eCRF	Electronic Case Record Form
ECP	Eosinophilic Cationic Protein
EASI	Eczema Area and Severity Index
EMA	European Medicines Agency
FDA	Food and Drug Administration
FDAAA	Food and Drug Administration Clinical Results Disclosure Requirements
GSK	GlaxoSmithKline
IA	Interim Analysis
ICH	International Conference on Harmonization
IDSL	Integrated Data Standards Library
IGA	Investigator's Global Assessment
IGE	Immunoglobulin
ITT	Intent-To-Treat
MCMC	Markov-Chain-Monte-Carlo
MMRM	Mixed Model Repeated Measures
NRS	Numeric Rating Scale
PCI	Potential Clinical Importance
PD	Pharmacodynamic
PDMP	Protocol Deviation Management Plan
PK	Pharmacokinetic
PRO	Patient reported Outcomes
QC	Quality Control
RAP	Reporting & Analysis Plan
SAC	Statistical Analysis Complete
SDTM	Study Data Tabulation Model
SOP	Standard Operation Procedure
TARC	Activation-regulated Chemokine
TA	Therapeutic Area
TFL	Tables, Figures & Listings

12.8.2. Trademarks

Trademarks of the GlaxoSmithKline Group of Companies
NONE

Trademarks not owned by the GlaxoSmithKline Group of Companies
SAS

12.9. Appendix 9: List of Data Displays

12.9.1. Data Display Numbering

The following numbering will be applied for RAP generated displays:

Section	Tables	Figures
Study Population	1.1 to 1.10	N/A
Efficacy	2.1 to 2.7	N/A
Safety	3.1 to 3.40	3.1 to 3.2
Pharmacokinetic	4.1	4.1 to 4.2
Pharmacodynamic and Biomarker	5.1 to 5.2	5.1 to 5.2
Section	Listings	
ICH Listings	1 to 26	
Other Listings	27 to 40	

12.9.2. Mock Example Shell Referencing

Non IDSL specifications will be referenced as indicated and if required example mock-up displays provided in [Appendix 10: Example Mock Shells for Data Displays](#).

Section	Figure	Table	Listing
Study Population	POP_Fn	POP_Tn	POP_Ln
Efficacy	EFF_Fn	EFF_Tn	EFF_Ln
Safety	SAFE_Fn	SAFE_Tn	SAFE_Ln
Pharmacokinetic	PK_Fn	PK_Tn	PK_Ln
Pharmacodynamic and Biomarker	PD_Fn	PD_Tn	PD_Ln

NOTES:

- Non-Standard displays are indicated in the 'IDSL / Example Shell' or 'Programming Notes' column as '[Non-Standard] + Reference.

12.9.3. Deliverables

Delivery [Priority] [1]	Description
SAC	Final Statistical Analysis Complete

NOTES:

1. Indicates priority (i.e. order) in which displays will be generated for the reporting effort

12.9.4. Study Population Tables

Study Population Tables					
No.	Population	IDSL/ Example Shell	Title	Programming Notes	Deliverable
Subject Disposition					
1.1.	ITT	ES1	Subject Status and Reason for Study Withdrawal	ICH E3, FDAAA, EudraCT	SAC
1.2.	ITT	SD1	Summary of Treatment Status and Reasons for Discontinuation of Study Treatment	ICH E3	SAC
1.3.	Screened	ES6	Summary of Screening Status and Reasons for Screen Failure	Journal Requirements Add Footnote "Note: Re-screened participants who have been randomised are included both in ENROLLED as well as FAILED category.	SAC
1.4.	Enrolled	NS1	Summary of Number of Participants Enrolled by Country and Site ID	EudraCT/Clinical Operations	SAC
Population Analysed					
1.5.	Screened	SP1	Summary of Study Populations	IDSL	SAC
Demographic and Baseline Characteristics					
1.6.	ITT	DM1	Summary of Demographic and Baseline Characteristics	ICH E3, FDAAA, EudraCT Include: Baseline Eosinophil counts and Fitzpatrick skin type	SAC
1.7.	ITT	DM11	Summary of Age Ranges	EudraCT Note: Include Age categories: Adult (18 – 64 years), >=65 – 84 years and >=85 years.	SAC
1.8.	ITT	DM5	Summary of Race and Racial Combinations	ICH E3, FDA, FDAAA, EudraCT	SAC

Study Population Tables					
No.	Population	IDSL/ Example Shell	Title	Programming Notes	Deliverable
Prior and Concomitant Medications					
1.9.	ITT	MH1	Summary of Past Medical Conditions	ICH E3	SAC
Exposure					
1.10.	Safety	POP_T1	Summary of Exposure to Study Treatment	ICH E3	SAC

12.9.5. Efficacy Tables

Efficacy: Tables					
No.	Population	IDSL/ Example Shell	Title	Programming Notes	Deliverable
IGA					
2.1.	ITT	EFF_T1	Bayesian Posterior Probability for Comparison between Mepolizumab and Placebo	Note: Non-Responder imputation will be used	SAC
2.2.	ITT	EFF_T2	Number (%) of Participants in Each Category of the Investigator's Global Assessment Scale at Each Visit		SAC
2.3.	ITT	EFF_T3	Summary of Proportion of Participants with IGA Score of 0 or 1 and at Least a 2-Grade Improvement from Baseline at Each Visit	Note: Non-Responder imputation will be used	SAC
EASI					
2.4.	ITT	EFF_T4	Summary of Change from Baseline/Percent Change from Baseline in EASI Score at Each Visit	Note: CFB, %CFB in bylines	SAC
2.5.	ITT	EFF_T4	Summary of Change from Baseline/Percent Change from Baseline in EASI Score at Each Visit by Baseline Blood Eosinophil Count Quartiles	Note: Include Quartiles categories as $\leq Q1(x)$, $>Q1(x)$ - $\leq Q2$, $>Q2(x)$ - $\leq Q3(x)$ and $>Q3(x)$. Include all quartiles value(x)	SAC
2.6.	ITT	EFF_T5	Summary of Proportion of Participants with $\geq 50\%$ and $\geq 75\%$ Improvement in EASI Score from Baseline at Each Visit	Note: $\geq 50\%$, $\geq 75\%$ improvement in bylines.	SAC
Patient Reported Outcomes					
2.7.	ITT	EFF_T4	Summary of Change from Baseline in Weekly Average of Daily Itch/pruritus NRS Score (based on Item #1 of Daily Sign and Symptom Severity Diary) at Each Visit	Includes Baseline values. Note: Mean change from baseline will be presented to only Week 4, 8, 12, 16 and 20	SAC

12.9.6. Safety Tables

Safety: Tables					
No.	Population	IDSL / Example Shell	Title	Programming Notes	Deliverable
Adverse Events (AEs)					
3.1.	Safety	AE1	Summary of All On-Treatment Adverse Events by System Organ Class and Preferred Term	ICH E3	SAC
3.2.	Safety	AE1	Summary of All Post-Treatment Adverse Events by System Organ Class and Preferred Term	ICH E3	SAC
3.3.	Safety	AE15	Summary of Common (>=3%) On-Treatment Non-Serious Adverse Events by System Organ Class and Preferred Term (Number of Participants and Occurrences)	FDAAA, EudraCT	SAC
3.4.	Safety	AE1	Summary of Adverse Events Reported on the Day of Dosing by System Organ Class and Preferred Term		SAC
3.5.	Safety	AE1	Summary of On-Treatment Adverse Events by Highest Binding Antibody Result		SAC
Serious and Other Significant Adverse Events					
3.6.	Safety	AE16	Summary of On-Treatment Serious Adverse Events by System Organ Class and Preferred Term (Number of Participants and Occurrences)	FDAA, EudraCT	SAC
3.7.	Safety	AE16	Summary of Post-Treatment Serious Adverse Events by System Organ Class and Preferred Term (Number of Participants and Occurrences)	FDAA, EudraCT	SAC
3.8.	Safety	AE3	Summary of Fatal Serious Adverse Events by Overall Frequency		SAC
Adverse Events of Special Interest (AESI's)					
3.9.	Safety	SAF_T1	Summary of On-Treatment Adverse Events of Special Interest Reported by the Investigator as Meeting the Criteria for Anaphylaxis		SAC

CONFIDENTIAL

205050

Safety: Tables					
No.	Population	IDSL / Example Shell	Title	Programming Notes	Deliverable
3.10.	Safety	SAF_T2	Summary Profile of On-Treatment Adverse Events Reported by the Investigator as Meeting the Criteria for Anaphylaxis	Produced only if more than one AESI reported in this category.	SAC
3.11.	Safety	SAF_T1	Summary of On-Treatment Adverse Events of Special Interest Reported by the Investigator as Systemic Reactions - Allergic (Type I Hypersensitivity) and Other Systemic		SAC
3.12.	Safety	SAF_T2	Summary Profile of On-Treatment Adverse Events Reported by the Investigator as Systemic Reactions - Allergic (Type I Hypersensitivity) and Other Systemic	Produced only if more than one AESI reported in this category.	SAC
3.13.	Safety	SAF_T1	Summary of On-Treatment Adverse Events of Special Interest Reported by the Investigator as Systemic Reactions - Allergic (Type I Hypersensitivity)		SAC
3.14.	Safety	SAF_T2	Summary Profile of On-Treatment Adverse Events Reported by the Investigator as Systemic Reactions - Allergic (Type I Hypersensitivity)	Produced only if more than one AESI reported in this category.	SAC
3.15.	Safety	SAF_T1	Summary of On-Treatment Adverse Events of Special Interest Reported by the Investigator as Systemic Reactions - Other Systemic		SAC
3.16.	Safety	SAF_T2	Summary Profile of On-Treatment Adverse Events Reported by the Investigator as Systemic Reactions - Other Systemic	Produced only if more than one AESI reported in this category.	SAC
3.17.	Safety	SAF_T1	Summary of On-Treatment Adverse Events of Special Interest Reported by the Investigator as Local Injection Site Reactions		SAC
3.18.	Safety	SAF_T2	Summary Profile of On-Treatment Adverse Events Reported by the Investigator as Local Injection Site Reactions	Produced only if more than one AESI reported in this category.	SAC
3.19.	Safety	SAF_T1	Summary of On-Treatment Adverse Events of Special Interest Categorized as Serious Cardiac, Vascular and Thromboembolic Events		SAC

Safety: Tables					
No.	Population	IDSL / Example Shell	Title	Programming Notes	Deliverable
3.20.	Safety	SAF_T2	Summary Profile of On-Treatment Adverse Events of Special Interest Categorised as Serious Cardiac, Vascular and Thromboembolic Events	Produced only if more than one AESI reported in this category.	SAC
3.21.	Safety	SAF_T1	Summary of On-Treatment Adverse Events of Special Interest Categorised as Serious Ischemic Events		SAC
3.22.	Safety	SAF_T2	Summary Profile of On-Treatment Adverse Events of Special Interest Categorised as Serious Ischemic Events	Produced only if more than one AESI reported in this category.	SAC
3.23.	Safety	SAF_T1	Summary of On-Treatment Adverse Events of Special Interest Categorised as Malignancies		SAC
3.24.	Safety	SAF_T2	Summary Profile of On-Treatment Adverse Events of Special Interest Categorised as Malignancies	Produced only if more than one AESI reported in this category.	SAC
3.25.	Safety	SAF_T1	Summary of On-Treatment Adverse Events of Special Interest Categorised as Opportunistic Infections		SAC
3.26.	Safety	SAF_T2	Summary Profile of On-Treatment Adverse Events of Special Interest Categorised as Opportunistic Infections	Produced only if more than one AESI reported in this category.	SAC
Laboratory: Chemistry					
3.27.	Safety	LB1	Summary of Chemistry Changes from Baseline	ICH E3 Includes Baseline values.	SAC
3.28.	Safety	LB3	Summary of Chemistry Shifts from Baseline Relative to Normal Range		SAC
3.29.	Safety	LB3	Summary of Emergent Chemistry Results (Relative to the Potential Clinical Concern Range)	ICH E3	SAC

Safety: Tables					
No.	Population	IDSL / Example Shell	Title	Programming Notes	Deliverable
Laboratory: Haematology					
3.30.	Safety	LB1	Summary of Haematology Changes from Baseline	ICH E3 Includes Baseline values.	SAC
3.31.	Safety	LB3	Summary of Haematology Shifts from Baseline Relative to Normal Range		SAC
3.32.	Safety	LB17	Summary of Emergent Haematology Results (Relative to the Potential Clinical Concern Range)	ICH E3	SAC
ECG					
3.33.	Safety	EG1	Summary of ECG Findings	The ECG findings to be summarized are the ECG interpretation, clinical significance of abnormal ECGs	SAC
3.34.	Safety	EG2	Summary of Change from Baseline in ECG Values by Visit	Includes Baseline values.	SAC
3.35.	Safety	EG10	Summary of Actual and Change from Baseline QTc(F) Values by Category	Category column will be replaced and created based on the information provided in the Section 8.4.1. For Anytime Post-Baseline, the highest post-baseline QTcF value and the change from baseline for this highest post-baseline QTc value is categorised	SAC
Vital Signs					
3.36.	Safety	VS1	Summary of Change from Baseline in Vital Signs	Includes Baseline values.	SAC
3.37.	Safety	VS3	Summary of Worst Case Vital Signs Results by PCI Criteria Post-Baseline Relative to Baseline		SAC

Safety: Tables					
No.	Population	IDSL / Example Shell	Title	Programming Notes	Deliverable
Immunogenicity					
3.38.	Safety	SAF_T3	Summary of Binding Antibody by Visit		SAC
3.39.	Safety	SAF_T4	Summary of Neutralising Antibody by Visit		SAC
3.40.	Safety	SAF_T5	Summary of Binding Antibody Assay Results: Highest Treatment Emergent Confirmatory Result Any Time Post Baseline		SAC

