- Subjects who are withdrawn from the study will complete an Early Withdrawal visit and then exit the study. See Section 5.4 and Table 3.

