5.4.2. Early Withdrawal from Study

The subject must **discontinue study treatment and be withdrawn from the study** for the following reasons:

- Subject demonstrates significant noncompliance with the study procedures. (See the SRM for examples.)
- Subject is lost to follow-up.
- Subject withdraws consent to participate in the study. If specified by the subject, the investigator should document the reason for withdrawal of consent.
- Study is terminated by the sponsor.
- Sponsor request (after discussion with the investigator) for reasons such as a significant protocol deviations or subject noncompliance.

Subjects who are **withdrawn from the study** will be asked to return to the clinic for an Early Withdrawal Visit providing that consent has not been withdrawn for subsequent visits.

If a subject withdraws from the study, he/she may request destruction of any samples taken, and the investigator must document this in the site study records. The investigator will record the primary reason for study withdrawal in the eCRF.

The following actions must be taken in relation to a subject who fails to attend the clinic for a required study visit:

- The site must attempt to contact the subject and re-schedule the missed visit as soon as possible.
- The site must counsel the subject on the importance of maintaining the assigned visit schedule and ascertain whether or not the subject wishes to and/or should continue in the study.
- In cases where the subject is deemed 'lost to follow up', the investigator or designee must make every effort to regain contact with the subject (where

possible, 3 telephone calls and if necessary a certified letter to the subject’s last known mailing address or local equivalent methods). These contact attempts should be documented in the subject’s medical record.

- Should the subject continue to be unreachable, only then will he/she be considered to have withdrawn from the study with a primary reason of “Lost to Follow-up”.

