7.4.1.1. Time period and Frequency for collecting AE and SAE information

- Any SAEs assessed as related to study participation (e.g., protocol-mandated procedures, invasive tests, or change in existing therapy) or related to a GSK product will be recorded from the time a subject consents to participate in the study up to and including any follow-up contact.
- AEs will be collected from the start of Study Treatment until the follow-up contact (i.e., the Week 20 visit) (See Section [7.4.1.3](#)), at the timepoints specified in the Time and Events Table (Section [7.1](#)).
- Medical occurrences that begin prior to the start of study treatment but after obtaining informed consent may be recorded on the Medical History/Current Medical Conditions section of the CRF.
- All SAEs will be recorded and reported to GSK within 24 hours, as indicated in [Appendix 11](#).

- Investigators are not obligated to actively seek AEs or SAEs in former study subjects. However, if the investigator learns of any SAE, including a death, at any time after a subject has been discharged from the study, and he/she considers the event reasonably related to the study treatment or study participation, the investigator must promptly notify GSK.

NOTE: The method of recording, evaluating and assessing causality of AEs and SAEs plus procedures for completing and transmitting SAE reports to GSK are provided in [Appendix 11](#).

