4. ANALYSIS POPULATIONS

Population	Definition / Criteria	Analyses Evaluated
All Screened	
 • All participants who were screened for eligibility 	
 • Study Population
Enrolled	
 • All participants who passed screening and entered the study including randomized participants 
Note: Screening failures (who never passed screening even if rescreened) and participants screened but never enrolled into the study (Reserve, Not Used) are excluded from the Enrolled population as they did not enter the study.
	
 • Study Population
Intent-to-Treat	
 • Comprises of all participants who are randomized and who received at least one dose of study treatment. 
Note: This population will be based on the treatment the participants are randomized to.
	
 • Study Population • Efficacy
Safety	
 • Comprises of all participants who received at least one dose of a study treatment will be included in the safety population. 
Note: This population will be based on the treatment the participants actually received.
	
 • Safety
PK	
 • All participants in the Safety population who received the active study treatment and had at least 1 non-missing PK assessment (Non-quantifiable [NQ] values will be considered as non-missing values). 	
 • PK
PD	
 • Comprises of all participants in the ITT population who received at least one dose of study treatment and who also have a baseline serum PD measurement and at least one post-treatment serum PD measurement. 	
 • PD

Population	Definition / Criteria	Analyses Evaluated
Biopsy	
 Comprises of all participants in the ITT population who have a baseline measurement and who also have at least one post-treatment PD biomarker measurement derived from skin biopsy samples. 	
 Biopsy sub-study

Refer to [Appendix 9](#): List of Data Displays which details the population used for each display.

Note: If any re-screened participants are randomized and received at least one dose then that subject will be counted in both Screened and ITT Populations.

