12.3. Appendix 3: Study Phases and Treatment Emergent Adverse Events

12.3.1. Study Phases

Safety assessments and events will be classified according to the time of occurrence relative to the first dose of investigational product.

The on-treatment phase for the presentation of exposure, adverse event and concomitant medications is defined as being from the day of the first administration to the day of the last administration of study treatment + another 28 days inclusive.

Treatment Phase	Definition
Pre-Treatment	Date < IP start date
On-Treatment	Event onset date is on/after IP start date & on/before IP stop date + 28 days (IP Start Date ≤ Date ≤ IP Stop Date + 28 days)
Post-Treatment	Event onset date is after the IP stop date + 28 (Date > IP stop date + 28)
IP = Investigational Product = Study Treatment	

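### Tables 3.2 and 3.7 express post-treatment AEs and SAEs as a percentage of everyone dosed, so subjects who left the study before that period began count as event-free

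*SAP*

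**What the plan says.** SAP Section 12.9.6 lists Table 3.2, "Summary of All Post-Treatment Adverse Events by System Organ Class and Preferred Term", and Table 3.7, its counterpart for serious events. Both have Safety in the population column, and neither has a programming note restricting who is counted. SAP Section 4 defines that population without any follow-up condition: "Comprises of all participants who received at least one dose of a study treatment will be included in the safety population". SAP Section 12.3.1 defines the post-treatment phase: "Event onset date is after the IP stop date + 28".

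On follow-up, the protocol treats two groups differently:

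- **Subjects who stop treatment only** (Section 5.4.1) are followed for 8 weeks after the last dose.
- **Subjects who leave the study** (Section 4.2.2) are not: "Subjects who are withdrawn from the study will complete an Early Withdrawal visit and then exit the study".

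Protocol Section 7.4.1.1 ends routine AE collection at the Week 20 visit. After discharge, sites need not look for events, but must report a related SAE that they learn of. Among the reasons for leaving the study in Section 5.4.2 is "Study is terminated by the sponsor". Section 5.4.1 gives the same reason for stopping treatment. SAP Section 1 records that the study was terminated for futility after the interim analysis.

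**The concern.** A percentage of subjects with an event in a given period should be read against the subjects who could have had an event recorded in it. Dosing is every 4 weeks, so someone who leaves the study while still being dosed normally does so within 28 days of the last dose, before the post-treatment phase starts. That subject cannot contribute to the numerator of Table 3.2 but is in its denominator.

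Separate post-treatment summaries are promised in Protocol Section 9.4.2, safety remains a secondary objective after termination (SAP Section 2.2.2), and Table 3.7 is tagged for public disclosure. No planned display gives the number of subjects observed in this phase. Table 1.10 counts exposure only to last dose + 28 days. Table 1.1 counts withdrawals without saying whether they came before that point. No exposure-adjusted rate is planned.

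**Working it through.** **Length of the window.** Week 12 is Day 85 (1 + 84). The on-treatment phase ends on Day 85 + 28 = 113, which agrees with the SAP Section 12.5.2 formula: 85 - 1 + 29 = 113 days. Week 20 is Day 141. A completer on the nominal schedule therefore has 141 - 113 = 28 post-treatment days. A subject who exits by last dose + 28 has none.

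**The only attrition figure in the documents.** Protocol Section 4.3 gives 56 randomized for 50 evaluable at 10% drop-out: 50 / (1 - 0.10) = 55.6, rounded up to 56. The stated figure reproduces.

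**Dilution.** Let N be the Safety subjects in an arm, m those who exit by last dose + 28, and x those with a post-treatment event, with no passively reported event among the m. Then

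- reported percentage = x / N
- percentage among those followed = x / (N - m)
- reported / followed = (N - m) / N = 1 - w, where w = m / N.

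For a true 20% among those followed:

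| w | Reported | Basis for w |
|---|---|---|
| 10% | 18% | ceiling: every planned drop-out leaves the study within 28 days of the last dose |
| 30% | 14% | assumed |
| 50% | 10% | assumed |

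In whole subjects, with 28 per arm, 3 exits and 5 subjects with events: 5/28 = 17.9% against 5/25 = 20.0%.

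**Between arms.** With equal true rates, the ratio of reported percentages is (1 - w1) / (1 - w2). Equal exits give 1.00 whatever their size. Assumed exits of 5% and 15% give 19% against 17% (0.95 / 0.85 = 1.12). Assumed exits of 10% and 30% give 18% against 14% (0.90 / 0.70 = 1.29).

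**The case against.** The strongest reply is that the effect is small, descriptive and mostly recoverable. At the planning ceiling, a true 20% of 28 subjects is 5.6 against 5.0 at 18%, about half a subject. No hypothesis is tested on these tables. Table 1.1 and the listings of withdrawals, exposure and AEs let a reader largely reconstruct follow-up. Keeping the dosed population as denominator is a common convention, and restricting it conditions on something that happens after randomization and weighs one day of follow-up like 28. All of this stands, and it limits the point to an improvement in presentation.

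Three stronger readings might be inferred, and the documents do not support them:

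- **That placebo is diluted more, through exits for lack of efficacy.** Worsening disease that needs a prohibited medication is a reason to stop treatment, not to leave the study (Protocol Sections 4.2.4 and 5.4.1). Those subjects are followed for 8 weeks and, if they stay, are observed in the window. Nothing shows that study exits differ by arm.
- **That termination removed a large share of subjects from follow-up.** Sponsor termination is listed under both 5.4.1 and 5.4.2, and the SAP does not say which applied. With 1:1 allocation, exits caused by termination should be roughly balanced, lowering both percentages but leaving their ratio near 1.
- **That nothing can be recorded after exit.** Related SAEs that the investigator learns of must still be reported, so Table 3.7 is not wholly blind there. This route is passive and does not cover non-serious events.

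Shells AE1 and AE16 are not reproduced in the SAP, so the denominator is read from the population column and from SAP Section 8.

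**Conclusion.** The point holds as a low-severity one. As specified, Tables 3.2 and 3.7 understate the post-treatment percentage among subjects followed by a factor (1 - w), and no planned display shows w. Under planned drop-out, w is at most about 10%, so 20% shows as 18%. That is a ceiling rather than an estimate, because a drop-out who stops treatment but completes follow-up adds nothing to w. Values of 30% to 50% are assumptions about what termination might have done. The two listings of sponsor termination in the protocol must be reconciled before anyone can say whether they are realistic.

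Distortion between arms is conditional on unequal exits and is not established. The conclusion rests on percentages being taken over the Safety N and on study exits while dosing falling within 28 days of the last dose.

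**What to change.** Derive one flag: Safety subjects whose last study contact is later than IP stop date + 28. In Tables 3.2 and 3.7, use the flagged number as the percentage denominator, print the Safety N beside it, and show the total post-treatment follow-up days per arm (last contact minus IP stop date + 28, summed). The days let a reader see partial coverage that a one-day threshold hides. List separately any SAE reported passively for a subject outside the flagged number, so that no event is lost and the numerator stays within the denominator. State in the SAP how subjects ongoing at termination were followed, and reconcile Protocol Sections 5.4.1 and 5.4.2 on that reason.

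The cost is one variable from disposition and visit dates, plus header rows and a short listing for two tables. The SAP already restricts denominators in this way: Table 3.40 covers only subjects without a positive pre-dose antibody result. The downside is a denominator that differs from the on-treatment tables, which stay unchanged.
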